Preliminary studies: Neuroimaging offers a precise and objective way to characterize the neural and molecular basis of the placebo response in humans. We have already established the utility of positron emission tomography (PET) with the μ -opioid selective ligand [^{11}C] carfentanil to investigate the neurobiology of placebo effects using a pain model [for a review, (Pecina and [name], 2014)]. Additionally, we have used the same methodology to define the neural bases of placebo effects in patients with Major Depressive Disorder (MDD) (PI: [name]). This study demonstrated that improvement of depressive symptoms in response to placebo administration was positively correlated with placebo-induced opioid release in the medial thalamus, anterior cingulate cortex (ACC), nucleus accumbens, and amygdala. These data show that placebo administration in patients with MDD is associated with increased opioid neurotransmission in regions implicated in emotion regulation. More recently, I have developed and piloted an fMRI experiment to characterize the cognitive mechanisms involved in placebo effects in patients with MDD. This fMRI task is specifically designed to record and modulate mood improvement by providing simulated neurofeedback in the context of an intravenous placebo administration with expectations of fast-acting antidepressant effects. In a pilot study using this task, patients with MDD who reported acute mood improvement in response to simulated positive neurofeedback showed increased blood oxygen level dependent (BOLD) responses in the ACC (Fig.

[figure not shown]

Fig. 1: Responses to the Simulated Real-time Neurofeedback fMRI task.
Simulated positive neurofeedback during this task resulted in 1) Acute mood improvement ($t=-2.8$, $p=0.03$) (left), and 2) Increased BOLD response in the rostral ACC (and also the dorsal and subgenual ACC) in placebo responders ($n=3$) compared to non-responders ($n=3$) (right).

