intravenous antidepressant", which will be either naloxone (NARCAN® injection, naloxone hcl injection. Endo Pharmaceuticals, Inc.) or saline (0.9% Sodium Chloride Injection). As previously described (Sprenger et al., 2011), naloxone will be administered in bolus of 0.15 mg naloxone per kg bodyweight or the same amount of saline, fifteen minutes before the experiment (Fig. 2). Because of the relatively short half-life of naloxone, an additional constant intravenous infusion (dose of 0.2 mg/kg/h or saline for the duration of the fMRI experiment) will be administered. To control for the effects of naloxone on blood pressure, the participants' blood pressure will be determined directly before and 5 minutes after drug application and at the end of the experiment.

Inside of the scanner, participants will undergo the "Simulated Real-Time Neurofeedback" fMRI task (Fig.2), which consist of periods of anticipation of "drug" or "drug-free" infusion (10s), followed by periods of simulated positive or negative neurofeedback (16s). Before the experiment, patients will be trained to expect positive neurofeedback and acute mood improvement in response to each "drug" infusion and negative neurofeedback and acute mood-worsening in response to each "drug-free" infusion trial. The experiment will consist of six 7-minute runs of 12 trials counterbalanced within and between runs. After the experiment, we will assess the task's credibility and patients who did not believe the experiment will be excluded from the study. All newly collected fMRI data will be analyzed using standard procedures (Ashburner, 2007). At the group-level, a random effects analysis will determine the main effects of the valance (positive versus negative neurofeedback) resulting in statistical parametric maps (t or F statistics), which will be thresholded with height and extent values generated by Monte Carlo simulations with 3dClustSim to protect against overall type I error at $p < 0.05$. To control for potential confounders, sex and depression severity will be entered as covariates in statistical models. The whole-brain analyses will be complemented by hypothesis-driven analyses in the rACC. Average BOLD signal within the rACC will be extracted and regressed against variables of interest.

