Of the 25 enrolled participants who received the naltrexone/placebo pill, two dropped out prior to scanning – one who was claustrophobic and another who had a positive pregnancy test. We excluded three additional participants who did not complete their placebo session. The final sample size for the contextual framing task was 20 for the placebo session, and 17 for the naltrexone session (thee participants did not complete the fMRI session naltrexone session, but their results from their placebo session were still included in the analysis). The final sample size for the antidepressant placebo fMRI task was 20 for both sessions.

Contextual Framing fMRI Task

The contextual framing task (Figure 1B) was iteratively refined as a simpler version of a similar task utilized by Mobbs and colleagues [39]. In this mixed block/event-related design, participants saw an emotionally evocative/salient contextual image for 2 seconds (Context phase) followed by the rating of the valence of an ambiguous emotional expression for 3 seconds (Emotion & Rating). The jittered inter-trial interval was ~ 3 seconds (2-6s range, S.D.=1.1)].

For the contextual images, we used a total of 72 emotionally evocative color photographs (36 pleasant and unpleasant images) from the International Affective Picture System (IAPS) database [44], which contains normalized scores of valences (pleasant = 9, unpleasant =1) and arousal (high = 9, low = 1) for all the images. Based on these scores, we selected 72 contextual images with high or low valence scores (pleasant > 7.3 and unpleasant < 3.4) and moderate arousal score (less than 6) to avoid excessively salient stimuli. This normalized image set provided the image-context for influencing the rating of ambiguous faces.

We then generated three types of emotional faces with ambiguous expressions from the NIM-STIM database (<http://www.macbrain.org/resources.htm>). First, we selected images of 48 individuals' faces that had a neutral facial expression. Then, the neutral face image was morphed with the same individuals' face image with a happy or fearful expression to generate ambiguous faces using a face-morphing software (Fantamorph 2.5). To maintain the ambiguity of facial expression, we merged morphed only 20% of happy or fearful face to with the neutral face.

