MRI First Level Analysis of the Antidepressant Placebo fMRI Task: We constructed four event regressors: infusion event, expectancy ratings event, neurofeedback event and mood ratings event. We constructed two additional regressors for the expectancy manipulation, coded as 1 or -1 ("antidepressant" infusion cue or calibration no-infusion cue, respectively) and the reinforcement manipulation, coded as 1 or -1 (positive or baseline sham neurofeedback, respectively). The expectancy manipulation regressor was aligned to the infusion event and the expectancy ratings event, whereas the reinforcement manipulation event was aligned to the neurofeedback event and the mood ratings event. For all models we convolved boxcar regressors with the HRF and used general linear models using FSL FEAT for each run and participant.

Group Level Statistical Analysis. We conducted group level voxel-wise analyses using randomize in FSL. We used threshold-free cluster enhancement to determine significant clusters ($1-p > 0.05$). For each contrast we conducted one-sample t-tests during the placebo session only. We then conducted paired samples t-test for each contrast (Placebo > Naltrexone and Naltrexone > Placebo).

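### The only significance rule for the voxel-wise TFCE group tests is printed as 1-p > 0.05, which means p < 0.95, and the type of p is not stated

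*Combined protocol and SAP*

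**What the plan says.** The relevant text is the paragraph on Group Level Statistical Analysis, at the end of MRI Analysis. It is in the past tense and describes completed work.

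- Software: "We conducted group level voxel-wise analyses using randomize in FSL".
- Decision rule: "We used threshold-free cluster enhancement to determine significant clusters ($1-p > 0.05". No other threshold is given for these tests.
- Tests under that rule: "For each contrast we conducted one-sample t-tests during the placebo session only", followed by "We then conducted paired samples t-test for each contrast (Placebo > Naltrexone and Naltrexone > Placebo").

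The paragraph does not say whether p is corrected across voxels, and it states no division of the error rate between the two opposite drug contrasts.

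One other imaging error level appears in the document, in the description of the fMRI analysis for the naloxone plan. There the maps are to be "thresholded with height and extent values generated by Monte Carlo simulations with 3dClustSim to protect against overall type I error at $p < 0.05". That is a different thresholding method, attached to a different drug and task plan.

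**The concern.** A rule of the form 1-p > c is a normal way to threshold maps that store 1-p, but c then has to be close to 1. With c = 0.05 the printed rule excludes only results with p of 0.95 or more and gives no control at 5%. Reversing the inequality does not help, because 1-p < 0.05 is p > 0.95. The number itself has to change.

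The second gap does not depend on the digit. A voxel-wise p < 0.05 means one thing if it is corrected for the search over the brain and something much weaker if it is not. The paragraph leaves this open.

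At stake is the reading of every voxel-wise group map in that paragraph, including the placebo versus naltrexone comparison. The point goes no further than those maps.

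**Working it through.** **Inputs**

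- Printed rule: 1-p > 0.05 (Group Level Statistical Analysis).
- Tests covered: one-sample tests in the placebo session, and paired tests in both directions (same paragraph).
- Sample sizes: 20 placebo and 17 naltrexone sessions for the contextual framing task, and 20 in both sessions for the antidepressant placebo task (paragraph on the final sample size).
- Comparison level: 0.05, from the 3dClustSim text of the naloxone plan.

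**Step 1: the rule as an ordinary p cut-off**

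1-p > c is the same as p < 1-c.

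- As printed, c = 0.05: p < 1 - 0.05 = 0.95.
- With c = 0.95: p < 1 - 0.95 = 0.05.

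The printed rule does not reproduce a 0.05 level. The version with 0.95 reproduces it exactly.

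**Step 2: worked cases**

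| p | 1-p | Printed rule (1-p > 0.05) | Likely intended rule (1-p > 0.95) |
|---|---|---|---|
| 0.94 | 0.06 | passes | fails |
| 0.03 | 0.97 | passes | passes |

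**Step 3: error rate if p is family-wise corrected**

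Assume that, when there is no effect anywhere, the smallest corrected p in a map is approximately uniform. Per directional test:

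- printed rule: P(p < 0.95) = 0.95
- intended rule: P(p < 0.05) = 0.05
- ratio: 0.95 / 0.05 = 19

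**Step 4: single-voxel check by simulation**

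A null simulation of a one-sample (or paired-difference) t-test on normal data, with 200,000 replicates, gave these rejection rates:

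| n | p < 0.95, one direction | p < 0.95, either direction | p < 0.05, one direction | p < 0.05, either direction |
|---|---|---|---|---|
| 17 | 0.950 | 1.00 | 0.050 | 0.100 |
| 20 | 0.951 | 1.00 | 0.050 | 0.100 |

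The 1.00 is exact: at one voxel the two one-sided p values add to 1, so the smaller is at most 0.5 and always passes p < 0.95. The last column is the sum over two opposite tails, 0.05 + 0.05 = 0.10. These rates illustrate the rule at one voxel. They are not whole-brain error rates.

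**Step 5: if p is uncorrected**

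The chance of at least one false cluster in a map then exceeds 5% even with the digit repaired. The excess depends on the number of voxels searched and on their correlation, which the document does not give in usable form, so no figure is offered.

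**Step 6: does another passage repair the rule?**

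No. The 3dClustSim sentence makes 0.05 the likely intended level but concerns another method in another plan. The pilot result in the Fig. 1 legend, "Acute mood improvement ($t=-2.8$, $p=0.03"), shows only that small p values are treated as positive. The text also contains other typing slips, for example "thee participants did not complete the fMRI session naltrexone session". Both are compatible with a slip and neither states the TFCE rule.

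**The case against.** The strongest objection is that this is an erratum. A rule that lets p = 0.94 through cannot be what anyone means by significant, the intended level is easily guessed as 0.05, and in the most likely case nothing in the results changes. On this view the 19-fold figure describes a case that nothing in the document suggests happened. The evidence for a slip is also thin in places: p = 0.03 passes both versions of the rule and so cannot tell them apart, and a misspelt word says nothing about a numerical threshold. The 3dClustSim level is the better support.

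Much of this stands. The slip reading is by far the more plausible, the 19-fold figure belongs only to the unlikely case, and the pilot p value and the misspelling are weak evidence. None of it rescues the sentence, which is wrong as printed and is the only rule given for these tests. Nor does guessing the digit tell the reader whether p was corrected.

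A further objection is that adding per directional test to the corrected sentence settles a choice the authors did not state. The paragraph does run two separate directional contrasts, so the phrase describes what was done. It should be included knowingly: with 0.05 in each direction, the combined rate for the two-way drug comparison is about 0.10.

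**Conclusion.** The concern holds and should be fixed. It is certain that the printed threshold is wrong: it equals p < 0.95, and no other text corrects it. That it is a slip for 1-p > 0.95 is a well-supported inference that the document does not confirm.

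The size depends on what was run:

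- **Slip, family-wise corrected p < 0.05 used (most likely):** no change to any result.
- **Printed rule applied to corrected p (unlikely):** about 95% of null directional tests declared significant instead of 5%, assuming an approximately uniform corrected p under the null.
- **Uncorrected p used:** map-wise error above 5%, by an amount that cannot be calculated from the document.

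The document does not show which of these holds. The absence of a statement on correction is secondary as a finding, but it is the part a reader cannot fill in by inference.

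**What to change.** 1. Because the work is reported as completed, first check in the analysis code which cut-off was applied and whether it was applied to corrected or uncorrected p.
2. If family-wise corrected p < 0.05 was used, change the sentence to say that clusters were judged significant at TFCE family-wise-error-corrected p < 0.05 (1-p > 0.95) per directional test. This makes plain that the two drug contrasts each carry 0.05. If the authors intended 0.05 across both directions, they should say so.
3. If the printed rule or uncorrected p was used, re-threshold the maps at family-wise corrected p < 0.05, state that rule, and report any clusters that drop out.

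The cost is one check of the code and one corrected sentence. No new data are needed, and re-thresholding arises only under step 3.
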